Statistical Considerations	
The primary efficacy analysis will be performed on all pre-defined analysis populations comparing the RBX2660 arm to the Placebo arm, Intent-to-Treat (ITT), modified Intent-to-Treat (mITT) and Per-Protocol (PP). However, the determination of meeting the pre-defined primary efficacy endpoint will utilize the mITT population results. The primary endpoint analysis will be based on Pearson's chi-square test with a 0.05 alpha level for this comparison. Secondary efficacy endpoints will also be completed on all analysis populations. Finally, all safety analyses will be performed on the Safety population (SP) which includes all subjects in whom a blinded enema was at least opened and attempted.
 
A primary efficacy and safety analysis will be conducted when all subjects have completed their 8-week follow-up assessment after receiving the blinded treatment. Safety analysis will be completed for safety endpoints defined at or prior to 8 weeks following blinded treatment along with any longer term safety data available at the time of analysis. One or more interim analyses will be conducted to evaluate the primary efficacy endpoint for possible early study stopping for success or futility. The first interim analysis will occur after a minimum of 160 subjects have been treated and evaluated for efficacy. A second interim analysis could occur when 220 subjects have been treated and evaluated for efficacy if success is not achieved at the first interim analysis. The details of the planned interim analyses are included in the statistical analysis plan.
 
Final long-term safety results as well as unblinded RBX2660 efficacy data will be analyzed and reported in a final report after the last subject has completed the 6-month follow-up visit for their study treatment. This includes 6-month follow-up after an unblinded RBX2660 study treatment. At that time the study will be considered complete.

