7.13.3. Reporting AEs to FDA and Health Canada

Rebiotix will report adverse events to FDA and Health Canada as required by applicable regulations. All adverse events will be reported in the annual and final clinical study reports.

8. Sample Size and Statistical Considerations

This study has a Statistical Analysis Plan which contains complete details of the statistical methodology and analyses that will be employed for this study.

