8.1. Assessment of Efficacy

The primary efficacy parameter is treatment success, defined as the absence of CDI diarrhea through 8 weeks after completing a study treatment. Efficacy assessments will occur at the 1-, 4- and 8-week office visits.

Recurrence of CDI after 8 weeks from completion of the assigned study treatment is considered a new *C. difficile* infection, as defined by the Centers for Disease Control (CDC website http://www.cdc.gov/hai/eip/cdiff_techinfo.html; published August 30, 2012; accessed October 02, 2016).

Primary Efficacy Endpoint: Recurrence of CDI within 8 weeks of blinded treatment.

The primary efficacy analysis will be performed on all pre-defined analysis populations comparing the RBX2660 arm to the Placebo arm, Intent-to-Treat (ITT), modified Intent-to-Treat (mITT) and Per-Protocol (PP). However, the determination of meeting the pre-defined primary efficacy endpoint will utilize the mITT population results. The primary analysis of the study will be a Bayesian hierarchical model, which formally incorporates data from a previous randomized Phase 2b study (Protocol 2014-01) of RBX2660. This analysis will demonstrate the efficacy of RBX2660 by showing a sufficiently high posterior probability that the rate of success in the treatment group is superior to the rate of success in the control group. Secondary efficacy endpoints will also be completed on all analysis populations. Finally, all safety analyses will be performed on the Safety

population (SP) which includes all subjects in whom a blinded enema was at least opened and attempted.

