6.4 Efficacy Variables

6.4.1 Primary Efficacy Endpoint

The primary efficacy endpoint is the recurrence of CDI within 8 weeks of blinded treatment. The primary analysis of the study will be a Bayesian hierarchical model, which formally incorporates data from a previous randomized Phase 2B study (Protocol 2014-01) of RBX2660. This analysis will demonstrate the efficacy of RBX2660 by showing a sufficiently high posterior probability that the rate of success in the treatment group is superior to the rate of success in the control group.

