6.4.2 Secondary Efficacy Endpoint

The secondary efficacy endpoint is the recurrence of CDI through 6 months after blinded treatment. This will be analyzed as the difference in time to CDI event between RBX2660 and Placebo following blinded treatment through 6 months of follow-up. This analysis will only be

analyzed if statistical significance ($p < 0.05$) is demonstrated for the primary efficacy endpoint. These endpoints will be tested at a two-sided 0.05 significance level.

The null hypothesis of interest is that there is no difference between RBX2660 and Placebo treated subjects in the probability of CDI at any time point during the 6 months of follow-up. The alternative is that there is a difference in the probability of CDI at any time point during 6 months of follow-up.

The power to detect the difference between RBX2660 and Placebo treatment at 6 months was estimated by 10,000 simulations of time to event data, with 104 subjects per treatment group. The data was simulated assuming the exponential distribution with the rate parameter lambda estimated using the 8-week success rates of 69% and 47% for RBX2660 and Placebo, respectively. Using the log-rank test, the power to detect the difference between the two groups at 6 months was 99.5%.

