7.6 Analysis of Efficacy

7.6.1 *Analyses Supporting the Primary Efficacy Endpoint*

7.6.1.1 *Treatment Success*

A hierarchical, closed-testing procedure will be utilized for the primary endpoint and secondary endpoints. Analyses of the single primary endpoint, recurrence of CDI within 8 weeks of blinded treatment, will be analyzed as the proportion of treatment success of Group A Placebo (P_{PLA}) and Group B RBX2660 (P_{RBX}). This analysis will be performed on the ITT, mITT and PP populations, with the mITT being the analysis of import for reporting purposes.

The primary efficacy analysis will be a Bayesian hierarchical model which formally incorporates data from the previous Phase 2B study (Protocol 2014-01) of RBX2660. Study success will be declared if the posterior probability of superiority exceeds 0.99943 at the first two interim analysis. If the trial continues to the maximum enrollment, the success criteria will be chosen so that the overall alpha is a nominal 0.00125. Success at this level is considered appropriate for approval based on results from a single study. If success at this level is not met at the final analysis, success may also be declared if the posterior probability exceeds 0.97706. Success at this secondary threshold still constitutes a successful study, although it may not be sufficiently strong evidence to request regulatory approval based on a single study without further FDA discussion. Details regarding the analysis can be found in Section 10 (Bayesian Analysis Plan).

The secondary endpoints will be analyzed using a hierarchical testing approach if sufficient evidence is found to claim study success.

The primary efficacy analysis will be conducted when all subjects in each group reach their 8-week assessment following blinded treatment or early termed from the study. Full study results in the form of a final analysis and report will be completed once the last subject has completed the 6-month telephone assessment, at which time the study will be considered complete. This includes subjects receiving unblinded RBX2660 due to a documented treatment failure.

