7.6.1.2 Sensitivity Analysis for the Primary Efficacy Endpoint

The primary efficacy analysis will be repeated using the ITT and PP population to assess the sensitivity of the primary endpoint regardless of the outcome of the mITT primary efficacy analysis. The ITT analysis will serve as the conservative analysis as it considers all subjects who exit prior to the 8-week efficacy assessment as treatment failures regardless of treatment failure documentation.

Three groups of sensitivity analyses will be performed to assess the sensitivity of the results to the borrowing of historical data from the previous Phase 2B study (Protocol 2014-01) of RBX2660.

- 1) A Pearson's chi-square test will be used to test the null hypothesis that the response rate in the treatment group is equal to that of the control group. In addition, two-sided 95% confidence intervals for the difference in response rate between arms will be calculated using a normal distribution approximation. This sensitivity analysis will be conducted using the mITT, ITT, and PP populations using data from the 2017-01 study only.
- 2) Sensitivity of the primary analysis (Bayesian analysis) to the analysis population (ITT, PP) using Bayesian analysis.
- 3) Sensitivity of the primary analysis (Bayesian analysis) to the following different sensitivity analysis populations from the 2014-01 study using Bayesian analysis. The **2014-01 Sensitivity Analysis Population #1** represents the ITT population from the 2014-01 study, and the **2014-01 Sensitivity Analysis Population #2** represents the

population used for the primary analysis inclusive of one subject in Group C who was exposed to product but did not receive the full enema.

2014-01 Sensitivity Analysis Population #1				2014-01 Sensitivity Analysis Population #2			
2014-01 Treatment Group	# Subjects	# Responders	Response Rate	2014-01 Treatment Group	# Subjects	# Responders	Response Rate
A	45	25	0.556	A	41	25	0.610
B	44	19	0.432	B	44	19	0.432
C	44	25	0.568	C	43	25	0.581

Efficacy analysis will be repeated without the borrowing of historical data from the Phase 2B study (Protocol 2014-01) using the mITT, ITT, and PP populations.

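### The Protocol Synopsis and SAP 6.4.2 still carry chi-square and p-value decision rules, although the governing primary analysis is Bayesian

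*Protocol*

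**What the plan says.** **Primary analysis.** The Synopsis, under Statistical Considerations, states: "The primary endpoint analysis will be based on Pearson's chi-square test with a 0.05 alpha level for this comparison". Protocol 8.1 has a nearly identical paragraph, but in that position it states: "The primary analysis of the study will be a Bayesian hierarchical model, which formally incorporates data from a previous randomized Phase 2b study". SAP 6.4.1 agrees with 8.1: "The primary analysis of the study will be a Bayesian hierarchical model, which formally incorporates data from a previous randomized Phase 2B study". SAP 7.6.1.1 and section 10 give the thresholds. These are a posterior probability of superiority above 0.99943 at the interims and an updated single-study threshold at the final analysis. Failing the latter, "success may also be declared if the posterior probability exceeds 0.97706", and 7.6.1.1 treats that result as a successful study. Pearson's test of the primary endpoint appears in SAP 7.6.1.2 as the first of three groups of sensitivity analyses: "This sensitivity analysis will be conducted using the mITT, ITT, and PP populations using data from the 2017-01 study only".

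**Gate to the secondary endpoint.** SAP 6.4.2 allows the secondary endpoint to be "analyzed if statistical significance ($p < 0.05$) is demonstrated for the primary efficacy endpoint". SAP 7.6.1.1 says: "The secondary endpoints will be analyzed using a hierarchical testing approach if sufficient evidence is found to claim study success". SAP 7.6.2 opens it when the primary null hypothesis is rejected, and SAP 8.7 points back to 7.6.1.1.

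**Precedence.** Protocol section 8 opens with: "This study has a Statistical Analysis Plan which contains complete details of the statistical methodology and analyses that will be employed for this study". Neither document says that section 8.1 or the SAP overrides the Synopsis.

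**The concern.** One protocol names two primary analyses, and one SAP contains two gates to the secondary endpoint. A reader who relies on the Synopsis would judge the trial by a frequentist test on its own data. A reader of Protocol 8.1 or the SAP would judge it by a posterior probability that borrows from study 2014-01. A reader of SAP 6.4.2 would look for a p-value that the primary analysis does not produce. The only planned p-value comparing 8-week success proportions between arms is the sensitivity Pearson test. Using it could keep the secondary endpoint closed after 7.6.1.1 had declared study success.

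If the result fell between the rules, the current text would leave room to dispute what was pre-specified and whether the secondary test was confirmatory. The choice also affects how strong the evidence looks: at a 45% control rate with no effect, SAP section 10 reports a 4.2% chance of success with borrowing and 2.2% without.

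**Working it through.** **1. The texts side by side**

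| Place | Primary analysis | Gate to secondary endpoint |
|---|---|---|
| Protocol Synopsis | Pearson, 0.05 | – |
| Protocol 8.1 | Bayesian, posterior probability | – |
| SAP 6.4.1 | Bayesian, posterior probability | – |
| SAP 6.4.2 | – | p < 0.05 on primary |
| SAP 7.6.1.1 | Bayesian, 0.99943 / 0.97706 | study success |
| SAP 7.6.1.2 | Pearson as sensitivity only | – |
| SAP 7.6.2 | – | primary null rejected |
| SAP 8.7 | – | refers to 7.6.1.1 |
| SAP 10 | Bayesian; null tested by posterior probability | – |

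Because section 10 tests the null by the posterior probability, 7.6.2 is compatible with 7.6.1.1. Only the Synopsis sentence and the p-value in 6.4.2 are out of line.

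**2. The plan's own figures**

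*Sample size.* The inputs are 47% vs 69%, 2:1 allocation, two-sided 0.05 (one-sided 0.025) and 90% power. The pooled rate is (0.47 + 2 × 0.69)/3 = 0.6167.

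n(control) = [1.960 × √(1.5 × 0.6167 × 0.3833) + 1.282 × √(0.47 × 0.53 + 0.69 × 0.31/2)]² / 0.22² = 77.1, so 78 control and 234 in total.

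The plan says 240. At 80/160 the power is 91.0%, so the stated size reproduces.

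*Bayesian rule.* The section 10 posterior was rebuilt on a numerical grid with:
- Phase 2b data 19/44 (placebo) and 25/42 (one dose);
- N(0, 10²) priors on the two means;
- inverse-gamma priors in the SAP's location/weight form, (0.001, 0.1) for the control variance and (0.01, 0.01) for the effect variance.

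One million trials were simulated at 45% vs 60%, with looks at 107/53, 147/73 and 180/90 and no futility stop. Cumulative success was 0.141, 0.257, 0.354 and 0.833. SAP Table 4 gives 0.141, 0.257, 0.354 and 0.833.

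**3. One data set, two answers**

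At the final analysis take 98/180 on RBX2660 and 40/90 on placebo.
- Difference: 0.5444 − 0.4444 = 0.1000. Pooled rate: 138/270 = 0.5111.
- Standard error: √(0.5111 × 0.4889 × (1/180 + 1/90)) = 0.0645.
- z = 0.1000/0.0645 = 1.55, so Pearson p = 0.12: failure under the Synopsis.
- Posterior probability of superiority = 0.979, above 0.97706: success under SAP 7.6.1.1.

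Against 40/90, the posterior first passes 0.97706 at 98/180, and Pearson first reaches p < 0.05 at 103/180. Every count from 98 to 102 is a success under one text and a failure under the other.

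**4. How often the rules part at the final analysis**

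These are exact binomial enumerations at 180/90, comparing posterior > 0.97706 with Pearson two-sided p < 0.05 favouring RBX2660.

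| True rates (placebo vs RBX2660) | Bayesian | Pearson | Disagree |
|---|---|---|---|
| 45% vs 60% (close to Phase 2b) | 83.3% | 65.3% | 18.0% |
| 47% vs 69% (design) | 98.9% | 93.8% | 5.1% |
| 47% vs 47% (no effect) | 5.0% | 2.6% | 2.4% |

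Essentially all disagreement is Bayesian success with Pearson failure. Independent rebuilds with other numerical grids gave 17.5% to 18.0% in the first row, about 5.1% in the second and 2.2% to 2.4% in the third.

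**5. The gate in 6.4.2, read as Pearson**

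With both interim looks included and Pearson evaluated at the analysis where the trial ends, a study success under 7.6.1.1 has p ≥ 0.05 in 17.7% of trials at 45% vs 60% and 5.0% at 47% vs 69%.

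**The case against.** The strongest reply is that intent is already clear. Protocol section 8 sends the reader to the SAP, and Protocol 8.1 and four SAP sections give the same Bayesian primary analysis. SAP 7.6.1.2 labels Pearson as sensitivity. That stands, and it is why this is a correction and not an open design question. It does not remove the need for the correction, because no text gives the SAP precedence over the Synopsis, and both gate texts for the secondary endpoint are inside the SAP.

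Second, SAP 6.4.2 does not name Pearson; its p-value may be leftover shorthand for the primary endpoint having been met. That is fair. What is certain is that the p-value is undefined under the Bayesian primary. The 17.7% and 5.0% hold only under the Pearson reading.

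Third, the Synopsis leaves interim details to the SAP, so its 0.05 level should not be read as an interim rule. An example such as 67/107 vs 24/53 at the first interim (p = 0.037, posterior 0.996, below 0.99943) shows that the rules can also part in the other direction. It carries little weight here.

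Fourth, 180/90 assumes that all 270 treated subjects are evaluable, while the plan allows for 10% loss. The SAP's own simulations also use 270. At 160/80 the disagreement is somewhat larger: 20.4%, 7.1% and 2.6% in the three scenarios.

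**Conclusion.** The point holds and should be fixed. The Synopsis sentence and the p-value condition in SAP 6.4.2 are wrong as written, because each is a decision rule that contradicts the governing Bayesian rule. The two rules give opposite answers on realistic data.

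If the out-of-line text were followed, they would disagree at the final analysis in about 5% of trials at the design rates and about 18% at rates close to Phase 2b. These figures assume 180/90 evaluable subjects, the section 10 priors read in location/weight form, and Pearson at two-sided 0.05 favouring RBX2660. They measure the gap between the texts and do not show an error in the Bayesian design or the sample size.

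**What to change.** Make two edits.

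1. **Protocol Synopsis, Statistical Considerations.** Replace the Pearson sentence with: *The primary analysis is the Bayesian hierarchical model of Protocol 8.1 and SAP section 10, with the success thresholds given in SAP 7.6.1.1 and section 10; Pearson's chi-square is a sensitivity analysis of the primary endpoint.*

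2. **SAP 6.4.2.** Replace the p-value condition with: *study success is declared as defined in Section 7.6.1.1 (posterior >0.99943 at an interim analysis; at the final analysis, the updated single-study threshold or >0.97706).* A bare cross-reference to 7.6.1.1 would also do, since any result passing the updated threshold (for example 0.99931 in SAP Example Trial 3) also passes 0.97706.

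SAP 7.6.1.1, 7.6.2 and 8.7 need no edit. The cost is one sentence and one clause, with no added patients, data or analyses.

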1.1. Background

RBX2660 (microbiota suspension) is an intestinal microbial suspension prepared from human stool obtained from carefully and thoroughly screened healthy human donors. It is being studied for the treatment of recurrent *Clostridium difficile* infection (CDI). RBX2660 is prepared from a standardized amount of stool mixed with saline and a cryoprotectant. It is stored at the manufacturer in a frozen state and is shipped frozen to the clinical site for administration via enema.

The donor selection process is multifaceted in its original screening of candidate donors as well as the ongoing assessment of donated samples prior to release for use in a clinical study. Some of these measures include the following:

1. Donor qualification screening includes questions that specifically address risk factors for colonization with multi-drug resistant organisms (MDROs), and individuals at higher risk of colonization with MDROs are excluded from donation. Examples of persons at higher risk for colonization with MDROs include:
 - a. Health care workers
 - b. Persons who have recently been hospitalized or discharged from long term care facilities
 - c. Persons who regularly attend outpatient medical or surgical clinics
 - d. Persons who have recently engaged in medical tourism
2. Donor stool testing includes MDRO testing to exclude use of stool that tests positive for MDRO. The MDRO tests include at minimum extended spectrum beta-lactamase (ESBL)-producing *Enterobacteriaceae*, vancomycin-resistant *enterococci* (VRE), carbapenem-resistant *Enterobacteriaceae* (CRE), and methicillin-resistant *Staphylococcus aureus* (MRSA).
3. All drug product currently in storage has undergone screening and stool testing for MDROs as described above.
4. The informed consent process for subjects being treated with RBX2660 product as part of this study describes the risks of MDRO transmission and invasive infection as well as the measures implemented for donor screening and stool testing.

Rebiotix has concluded the first clinical study of RBX2660 (n=34) in an open-label, non-controlled Phase 2 study demonstrating the safety of the product. Additionally, Rebiotix has completed enrollment and interim reports of two Phase 2 clinical studies. Protocol 2014-01 is a prospective, multicenter, randomized, double-blinded, placebo-controlled, 3-arm Phase 2B study (n=127 treated) designed to demonstrate the efficacy and safety of RBX2660 for the treatment of recurrent CDI. Primarily, the Phase 2B

study compared the efficacy of RBX2660 to placebo, and secondarily compared the efficacy of two planned enemas of RBX2660 to one planned enema of RBX2660 with one enema of placebo. The study has completed enrollment and primary efficacy analysis and continues in long term follow-up. Protocol 2015-01 is an open label study comparing the efficacy and safety of two planned RBX2660 enemas (n=136 treated) to a historical control (n=110) is in long-term follow-up.

Finally, to complete the RBX2660 clinical development program, Rebiotix is initiating a Phase 3 study. The purpose of this Phase 3 study is to confirm the efficacy and safety of RBX2660 for the prevention of recurrent CDI in subjects who have had prior recurrent *Clostridium difficile* infection that was resolved with antibiotic treatment.

The study will be conducted in compliance with this protocol as approved by the federal Food and Drug Administration and each site's governing Institutional Review Board or Research Ethics Board (Canada); in accordance to relevant regulations in 21 CFR Part 11, 50, 54, 56 and 312; and the ICH E6 Good Clinical Practice: Consolidated Guidance.

1.2. Investigational Agent

RBX2660 (microbiota suspension) 50g/150mL in an enema bag within a brown opaque sleeve, which is to remain in place over the bag and tubing during administration and disposal. Each bag contains one dose. Each dose contains minimum 10^7 microbes/mL of suspension in a saline/polyethylene glycol 3350 vehicle.

Note: For this protocol, the term “Investigational Product (IP)” refers to both RBX2660 and the Placebo.

1.3. Placebo

The Placebo consists of 150 mL of normal saline, but without the polyethylene glycol 3350 or drug substance, human stool. It is supplied in an enema bag within a brown opaque sleeve, which is to remain in place over the bag and tubing during administration and disposal. Each bag contains one dose.

1.4. Preclinical Data

Fecal transplantation is being used today in many highly respected hospitals throughout the world with no significant reports of adverse events or other safety-related complications. Rebiotix has conducted an extensive literature review from the first published cases in 1958 (Eiseman et al., 1958) to the present. The literature presents significant evidence of the safe and effective use of FT for over 500 cases of recurrent *Clostridium difficile* infection (CDI) with no product-related adverse events reported to

date and only a few procedure-related events, none of which have occurred in subjects receiving FT via enema (Bakken, 2015). Based on the significant human clinical experience documented in the literature, it has been determined that preclinical studies are not warranted.

